6.4 STUDY INTERVENTION COMPLIANCE

Measures taken to ensure and document treatment compliance and IMP accountability include:

- Proper recording of treatment kit number as required on appropriate electronic case report form (e-CRF page for accounting purposes).
- All medication treatment kits (whether empty or unused) are returned by the participant at each visit when a treatment dispensing is planned:
 - The completed home dosing diary (returned to the site at each visit), returned treatment kit boxes and any unused prefilled syringes will be used for drug accountability purposes.
- The Investigator or designee tracks treatment accountability/compliance, either by home dosing diary, or by counting the number of used treatment kits and fills in the appropriate page of the participant treatment log.

The monitor in charge of the study then checks the data entered on the IMP administration page by comparing them with the IMP that has been retrieved and the participant treatment log form.

The Investigator or pharmacist will also keep accurate records of the quantities of the IMP received, dispensed, used, unused, and returned/destroyed. The product accountability and inventory form/system are to be updated each time IMP is dispensed.

All used, partially used, or unused treatments will be destroyed at each respective site, after accountability and reconciliation have been performed. The site must not destroy the unused IMP unless the Sponsor provides written authorization. Confirmation of destruction will be provided to the Sponsor.

6.5 CONCOMITANT THERAPY

Any medication or vaccine (including over-the-counter or prescription medicines, vitamins, and/or herbal supplements) that the participant is receiving at the time of enrollment or receives during the study must be recorded along with:

- Reason for use.
- Dates of administration including start and end dates.
- Dosage information including dose and frequency.

Prohibited concomitant therapy:

- Any biologic therapy (including experimental treatments and dupilumab) or any other biologic therapy/immunosuppressant.
- Treatment with live (attenuated) vaccine.
- Treatment with systemic corticosteroids (systemic corticosteroids can only be used to treat an asthma exacerbation, and are not allowed to be used for other conditions)

During the FU period the asthma treatment will be administered based on Investigator's medical judgment and normal clinical practice.

6.6 RESCUE MEDICINE

The SABA rescue medications may be used. The rescue medication will be administered as prescribed by the physician. Systemic corticosteroids are allowed for the treatment of asthma exacerbations. Although the use of rescue medications is allowed at any time during the study, every attempt should be made to perform all necessary measurements prior to the use of rescue medications. If SABA rescue medications are given prior to any measurements, including HRCT, the measurements should be performed after a wash-out time mentioned in [Table 4 \(Section 8.1\)](#). In case of severe asthma exacerbations treated with systemic corticosteroids, the visits can be postponed up to 1 week to ensure the wash-out period (Table 4) is completed before performing HRCT scan, FeNO, FOT, and spirometry. In case this is not possible (eg, a participant experiences an exacerbation shortly before the scheduled visit), the procedures can be performed as planned, but it should be recorded that the participant had recently taken systemic corticosteroids. The date and time of rescue medication administration as well as the name and dosage regimen of the rescue medication must be recorded.

6.7 DOSE MODIFICATION

Not applicable.

6.8 INTERVENTION AFTER THE END OF THE STUDY

Not applicable.

7 DISCONTINUATION OF STUDY INTERVENTION AND PARTICIPANT DISCONTINUATION/WITHDRAWAL

Withdrawal of consent for treatment (ie, treatment discontinuation at participant request) should be distinguished from (additional) withdrawal of consent for follow-up visits. The site should document any case of withdrawal of consent.

7.1 DISCONTINUATION OF STUDY INTERVENTION

7.1.1 Definitive discontinuation

In rare instances, it may be necessary for a participant to permanently discontinue study intervention. If study intervention is permanently discontinued, the participant will remain in the study to be evaluated for safety and efficacy. See the schedule of activities (SoA) for data to be collected at the time of discontinuation of study intervention ([Section 1.3](#)).

Discontinuation of study intervention for abnormal liver function should be considered by the Investigator when a participant meets one of the conditions outlined in the algorithm Increased in alanine aminotransferase (ALT) ([Section 10.5](#)) or if the Investigator believes that it is in best interest of the participant.

List of criteria for permanent discontinuation of study intervention

Every effort should be made to document the reason(s) for discontinuation of study intervention and this should be documented in the e-CRF.

Participants may be withdrawn from the study intervention for the following reasons:

- At their own request or at the request of their legally authorized representative (legally authorized representative means an individual or judicial or other body authorized under applicable law to consent on behalf of a prospective participant to the participant's participation in the procedure(s) involved in the research).
- If, in the Investigator's opinion, continuation in the study would be detrimental to the participant's well-being.
- At the specific request of the Sponsor.
- If the Emergency Unblinding transaction is performed by the Investigator (ie, at the site level).
- Pregnancy.
- Anaphylactic reactions or systemic allergic reactions that are related to IMP and require treatment.
- Any opportunistic infection, such as tuberculosis or other infections whose nature or course may suggest an immunocompromised status.
- Serum ALT >3 upper limit of normal (ULN) and Total Bilirubin >2 ULN (see [Section 10.5](#), Appendix 5).
- Serum ALT >5 ULN if baseline ALT ≤ 2 ULN or ALT >8 ULN if baseline ALT >2 ULN (see [Section 10.5](#), Appendix 5). "Baseline" refers to ALT sampled at baseline visit or, if baseline value is unavailable, to the latest ALT value before the baseline visit.

See the SoA ([Section 1.3](#)) for data to be collected at the time of intervention discontinuation and follow-up and for any further evaluations that need to be completed.

Any abnormal laboratory value will be immediately rechecked for confirmation before making a decision of definitive discontinuation of the IMP for the concerned participant.

Handling of participants after permanent study intervention discontinuation:

Participants who prematurely discontinue the study intervention (prior to completing the 24-weeks treatment period) should attend an ETD visit at earliest convenience with all procedures required at the EOT visit, except HRCT and IMP. In particular cases when the ETD visit is closed to a regular study visit, ETD could be merged and will replace the regular visit. In addition, the participants will be asked and encouraged to complete all the remaining study visits according to the visit schedule until and including the EOT visit (V5). Participants will be followed-up according to the study procedures specified in this protocol in SoA ([Section 1.3](#)). Under exceptional circumstances when a participant cannot come to the site for the scheduled visit, a phone contact can be made after sponsor approval is given. During the phone contact, at least information about AEs and concomitant medication should be collected.

All cases of permanent discontinuation of study intervention should be recorded by the Investigator in the appropriate pages of the e-CRF when considered as confirmed.

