a Participants who prematurely discontinue the study intervention (prior to completing the 24-week treatment period) should attend an Early Treatment Discontinuation (ETD) visit at earliest convenience with all the assessments planned for the End of Treatment visit (V5), except HRCT scans and IMP. In particular cases when the ETD visit is closed to a regular study visit, ETD could be merged and will replace the regular visit. In addition, the participants will be asked and encouraged to complete all the remaining study visits according to the visit schedule until and including the EOT visit (V5). Under exceptional circumstances when a participant cannot come to the site for the scheduled visit, a phone contact can be made after sponsor approval is given. During the phone contact, at least information about AEs and concomitant medication should be collected.

b Participants who prematurely discontinue the study should attend an Early Study Discontinuation (ESD) visit at earliest convenience with all the procedures planned for the End of Treatment Visit (Visit 5) except IMP. If the investigator considers that the time from the last HRCT scan exposure is not acceptable, the investigation will not be done.

c Post-treatment Follow-up: up to 12 Weeks or until the participants switch to commercialized dupilumab (or other biologic products), the call visit should be done first.

d Visit 6 will be a telephone visit. For the participants who switch to commercialized dupilumab (or other biologic products), the call visit should be done prior to the first injection with commercialized dupilumab (or other biologic products).

e Vital signs, including blood pressure (mmHg), heart rate (beats per minute), respiratory rate (breaths per minute), body temperature (degrees Celsius).

f A complete physical examination will include, at a minimum, assessments of the cardiovascular, respiratory, gastrointestinal and neurological systems and will be performed at V1, V2 and V5. Body weight (kg) will be measured at V1, V2 and V5. Height (cm) will be measured only at V1.

g Reversibility test: Three attempts may be performed during the screening period to meet the qualifying criteria for reversibility before randomization. This is only required if a reversibility test meeting eligibility criterion was not performed within 6 months prior to Visit 1.

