h Asthma Control Questionnaire-7 (ACQ-7): items 1 to 6 should be completed by the participant, independently from their physician, the study nurse or any other medical personnel and without any help from friends or relatives. The questionnaire should be completed by the participants before the consultation and/or clinical tests, in a quiet place. ACQ-5 scores (mean of the responses to the first 5 questions) and ACQ-6 (mean of the responses to the first 6 questions) will be derived from ACQ-7. The local values of FEV1 will be considered for the ACQ-7 scores. For the statistical analysis we will use centrally read values.

i Asthma Quality of Life Questionnaire with Standardized Activities [AQL Q(S)] should be completed by the participant, independently from their physician, the study nurse or any other medical personnel and without any help from friends or relatives. The questionnaire should be completed by the participants before the consultation and/or clinical tests, in a quiet place.

j FeNO should be conducted prior to spirometry and the participant should refrain from eating and drinking for ≥ 1 hour before the procedure. The test will be performed after a wash out period of bronchodilators according to their action duration as detailed in [Table 4 \(Section 8.1\)](#). Retesting of FeNO can be done one additional time during screening if the eligibility criterion for FeNO was not met at V1. FeNO will be rechecked at randomization visit (V2) for eligibility. Further details on the procedure for measuring FeNO will be provided in a separate instruction manual.

k Centrally read. Scans are respiratory gated to avoid variations in lung and airway volume, as per scans protocol. Further details on the HRCT scan will be provided in a separate instruction manual. The wash out time of the asthma controllers and rescue medication before HRCT and lung function assessments is detailed in [Table 4 \(Section 8.1\)](#). If HRCT scan cannot be performed at D1 due to logistic reasons, it can be scheduled the next day. In this particular situation the investigator should ensure that the IMP loading dose is administered after the HRCT scan, at D1+1 day. At visits, the HRCT scan can be done before spirometry or before post-BD FEV1 or after (in the latter case the wash-out period of SABA should be ensured), as per investigator's decision.

l FOT should be conducted prior to spirometry. Further details on FOT will be provided in a separate instruction manual.

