m Centrally read. Spirometry test should be performed before IMP administration, in the morning if possible, but if testing can only be done at another time during the day, then the testing should be done at approximately the same time of day at each visit throughout the study. Spirometry will be performed after a wash out period of bronchodilators according to their action duration as detailed in [Table 4 \(Section 8.1\)](#). This will be verified before performing the measurements. A participant who is unable to complete a successful spirometry effort as defined by ATS criteria or evaluated by the investigator or did not meet the eligibility criterion for pre-BD FEV1 at V1 can be retested one additional time during the screening period. For spirometry the investigator will assess the eligibility based on the FEV1 local values from V1 and V2 before randomization (the results from central reading will not be available on the same day). The recommendation is to perform the FeNO and FOT before spirometry

n Serum pregnancy test at screening visit (Visit 1) and urine pregnancy tests at the other visits using dipstick. A negative result must be obtained at Visits 1 and 2 for eligibility. In case of positive urinary test during the study, a serum pregnancy test should be performed as soon as possible to confirm the pregnancy. A urine pregnancy test will be performed at home at the end of follow-up visit.

o Retesting of eosinophil count is allowed up to three times during the screening period to meet inclusion criteria for showing eosinophil count ≥ 300 cells/microliter (cells/mL) (1.06) before randomization. This is only required if the participant does not have the blood eosinophil count measured within 6 months prior to V1 in the absence of OCS treatment.

p Hepatitis screening covering hepatitis B surface antigen (HBs Ag), total hepatitis B core antibody (total HBcAb) including IgM HBcAb; hepatitis C virus antibodies (HCvAb). In case of results showing HBsAg (negative) and HBcAb (positive), HBV DNA testing will be performed to rule out a false positivity or to clarify the serological status if the investigator finds it unclear to interpret in absence of known HBV infection. In case of results showing HCvAb (positive), HCV RNA testing may be performed to rule out a false positivity. Human immunodeficiency Virus (HIV) screening (Anti-HIV-1 and HIV-2 antibodies).

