7.2 PARTICIPANT DISCONTINUATION/WITHDRAWAL FROM THE STUDY

- A participant may withdraw from the study at any time at his/her own request or may be withdrawn at any time at the discretion of the Investigator for safety, behavioral, compliance, or administrative reasons. This is expected to be uncommon.
- Participants who prematurely discontinue the study, should attend an Early Study Discontinuation (ESD) visit at the earliest convenience with all the procedures planned for the End of Treatment Visit (Visit 5) except IMP, as shown in the SoA ([Section 1.3](#)). See SoA for data to be collected at the time of study discontinuation and follow-up and for any further evaluations that need to be completed. If the Investigator considers that the time from the last HRCT scan exposure is not acceptable, the investigation will not be done.
- The participant will be permanently discontinued both from the study intervention and from the study at that time.
- If the participant withdraws consent for disclosure of future information, the Sponsor may retain and continue to use any data collected before such a withdrawal of consent.
- If a participant withdraws from the study, he/she may request destruction of any samples taken and not tested, and the Investigator must document this in the site study records.

If participants no longer wish to take the IMP, they will be encouraged to remain in the study.

The investigators should discuss with them key visits to attend. The value of all their study data collected during their continued involvement will be emphasized as important to the public health value of the study.

Participants who withdraw from the study intervention should be explicitly asked about the contribution of possible AEs to their decision, and any adverse event (AE) information elicited must be documented.

All study withdrawals should be recorded by the Investigator in the appropriate screens of the e-CRF and in the participant's medical records. In the medical record, at least the date of the withdrawal and the reason should be documented.

In addition, a participant may withdraw his/her consent to stop participating in the study. Withdrawal of consent for intervention should be distinguished from withdrawal of consent for follow-up visits and from withdrawal of consent for non-participant contact follow-up, eg, medical record checks. The site should document any case of withdrawal of consent.

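### Pregnancy stops the study drug but, in the visible protocol, does not stop the later research HRCT scans, and no text puts the pregnancy test before the scan

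*Protocol*

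**What the plan says.** **Consequence of pregnancy.** Sections 7.1.1 and 8.3.5 and Appendix 4 (Section 10.4) stop the study drug. They add reporting and follow-up of the pregnancy but say nothing about imaging.

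**After stopping the drug.** Section 7.1.1 states: "If study intervention is permanently discontinued, the participant will remain in the study to be evaluated for safety and efficacy". The participant is to be "asked and encouraged to complete all the remaining study visits according to the visit schedule until and including the EOT visit (V5"). Section 2.3 places HRCT at D1, W4 and W24.

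**Early treatment discontinuation (ETD) visit.** HRCT is left out here, whatever the reason for stopping. If this visit falls near a scheduled one, the "ETD could be merged and will replace the regular visit".

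**ESD visit.** Section 7.2 asks for attendance "with all the procedures planned for the End of Treatment Visit (Visit 5) except IMP, as shown in the SoA". The only HRCT exception is in Schedule of Activities footnote b and Section 7.2: "If the investigator considers that the time from the last HRCT scan exposure is not acceptable, the investigation will not be done".

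**Testing.** Footnote n schedules a serum test at V1 and urine tests at the other visits. For entry, "A negative result must be obtained at Visits 1 and 2 for eligibility". Later, "In case of positive urinary test during the study, a serum pregnancy test should be performed as soon as possible to confirm the pregnancy". Appendix 4 also requires a test after a missed period or on suspicion of pregnancy.

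**Order within a visit.** Footnote k says "At visits, the HRCT scan can be done before spirometry or before post-BD FEV1 or after", subject to SABA wash-out. It does not mention the pregnancy test.

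**The concern.** The study exposes participants to two things they would not otherwise receive: the injection and the research CT. The pregnancy rules act on the first only. Section 8 adds that waivers are not permitted and that the Schedule of Activities must be followed. A site applying the written rules literally would therefore still have an HRCT on the list for a participant known to be pregnant, at W24 or at ESD. Withdrawing her for safety does not remove it, because withdrawal leads to the ESD visit.

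The second question is whether a pregnancy not yet known could be scanned on the day its test is due. Footnote k does not prevent that.

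The scan serves the research only. The radiation text (Section 2.3 and Appendix 10) discusses younger women because of breast exposure but does not mention pregnancy.

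**Working it through.** **1. Following a pregnant participant through the visits**

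| Pregnancy found | What the text provides | HRCT still listed |
|---|---|---|
| Around W4 | Drug stopped; ETD visit has no scan and may replace W4 | W24, or ESD |
| Around W12 | Drug stopped; ETD visit has no scan (none is due at W12) | W24, or ESD |
| Well before W24, between visits | Drug stopped; ETD visit has no scan | W24, or ESD |
| Around W24 | Drug stopped; ETD visit may replace W24 | None if merged |

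The ETD carve-out reaches that visit and any visit merged with it, but not a later W24 visit. This is the main gap.

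**2. Dose** (Section 2.3: 1.8 mSv per acquisition, two acquisitions per scan, three scans)

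- The protocol's total: 6 × 1.8 = 10.8 mSv, reproduced.
- One scan visit: 2 × 1.8 = 3.6 mSv, one third of the total.
- W4 and W24 together: 2 × 3.6 = 7.2 mSv. This needs a pregnancy that begins before W4 and both scans carried out.

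These are effective doses to the participant. They do not measure fetal exposure, which the documents do not give.

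**3. Expected pregnancies over 24 weeks**

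Formula: 97 × share of women of childbearing potential (WOCBP) × 24/52 × annual failure rate. The documents give 97 and a failure rate below 1% per year for consistent and correct use (Appendix 4). The WOCBP share (20% to 50%) and a typical-use rate of 5% per year are assumptions.

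| WOCBP share | 1% per year | 5% per year |
|---|---|---|
| 20% | 97 × 0.20 × 24/52 × 0.01 = 0.09 | 0.45 |
| 50% | 97 × 0.50 × 24/52 × 0.01 = 0.22 | 1.12 |

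**4. Size of the ordering gap**

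Assume that onset is uniform over the 24 weeks and that a missed period follows conception by about 2 weeks. Only conceptions in the last 2 weeks before W4 or before W24 then reach the scan without an earlier test required by Appendix 4: (2 + 2)/24 = 17%. Applied to step 3, this is 0.015 to 0.04 participants at 1% per year and 0.07 to 0.19 at 5% per year.

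**5. Power cost of omitting scans**

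Section 9.2 gives about 64% power for [s]iVaw with 87 evaluable participants (58 and 29), two-sample t-test, two-sided 0.05. That implies a standardised difference of 0.533. With two Week 24 scans lost:

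- both dupilumab (56/29): 63.5%
- one per arm (57/28): 62.7%
- both placebo (58/27): 61.9%

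**The case against.** The strongest reply is that this is an absence in the documents at hand, while the conduct of the scan is delegated elsewhere. Footnote k and Section 8.1 refer to a separate instruction manual, and the consent pages were not available. A pre-scan pregnancy check would naturally sit in either place. That stands, and it limits confidence.

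General provisions also help. Remaining visits are encouraged and not compulsory, off-treatment imaging is used only as available (Table 7), and the investigator works under GCP. Entry protection is good, with pregnancy excluded, highly effective contraception required and a test at every visit. A sensible investigator would very probably omit the scan. None of these provisions names pregnancy, however, and discretion cannot help when the pregnancy is not yet known.

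Three stronger readings are tempting, and the documents do not support them:

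- **That the protocol compels a pregnant participant to be scanned.** It does not. It fails to exempt her.
- **That two thirds of on-study pregnancies would meet their first test on a scan day.** Counting scheduled tests only, onset in D1–W4 or W12–W24 gives (4 + 12)/24 = 67%. Appendix 4 also requires a test after a missed period, so the figure for the ordering gap is nearer 17%.
- **That D1 is fully protected while W4 and W24 are not.** A negative V2 result is needed for eligibility, but the order of that test and the D1 scan is not stated either.

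**Conclusion.** The point holds for the visible text, chiefly as a missing exemption at W24 and ESD and only secondarily as a missing order of procedures. Probably 0 or 1 participant would be affected, usually with one scan visit of 3.6 mSv maternal effective dose. The frequency rests on an assumed WOCBP share and, at its upper end, an assumed 5% failure rate. The 17% rests on uniform onset and a 2-week interval to a missed period.

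A reader might infer a measured fetal harm; the documents allow no such statement. A reader might also infer that no safeguard exists anywhere; the HRCT manual, the consent form or local radiology rules may contain one. This is a cheap safety improvement for a rare event. It does not threaten the trial's conclusions.

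**What to change.** Add to footnote k, with cross-references in footnotes a, b and n and in Sections 7.1.1, 7.2 and 8.3.5:

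> In WOCBP, the urine pregnancy test scheduled at the visit must be performed and be negative before HRCT. No HRCT is performed at any visit, including ESD, once pregnancy is suspected or confirmed; other assessments may continue.

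The last clause matters for Week 24 FeNO, because a missing value there counts as non-response for the first primary endpoint (SAP Section 8.1.1).

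If the HRCT manual already holds this rule, cite it in footnote k and bring the ESD and post-discontinuation text into line.

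The urine test is already scheduled at D1, W4 and W24, so those visits need no new procedure. The cost is one or two missing scans, which the planned MMRM takes without imputation, and at most about two percentage points of [s]iVaw power if two are lost.
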